### **16.3.3. Primary Endpoint Analysis**

The primary endpoint (change of TSQM-9 convenience domain at week 12) will be analysed by a repeated measures analysis of variance adjusted for baseline factors (age, sex, disease duration, previous treatment duration, EDSS).

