In addition, routine clinical assessments will be performed in order to check the safety of the Peg-IFN ongoing treatment.

Laboratory Safety Assessments

At the Investigator's discretion, the following routine laboratory tests can be carried out, in order to monitor the safety profile of the ongoing treatment based on Peg-IFN:

- Hematology: RBC- WBC –Haemoglobin- Haematocrit- MCV- MCH – MCHC - Platelets Count – Lymphocytes- Monocytes – Neutrophils – Eosinophils – Basophils
- Blood chemistry: creatinine, blood urea nitrogen (BUN), alkaline phosphatase, ALT, AST, gamma-glutamyl-transferase (GGT).

A pregnancy hCG test (blood sample) will be performed at the baseline visit (T0) to exclude pregnancy, if applicable (it is not required if the subject is post-menopausal or surgically sterilized).

9. Missing data

For missing data in TSQM-9, MSTCQ and MusiQoI see paragraph Variable of analysis.

For the other variables no imputation technique will be apply.

10. Statistical analysis

The primary and secondary endpoints will be evaluated using a repeated measures ANOVA. The repeated measures ANOVA is used to compare group means on a dependent variable across repeated measurements of time. This statistical method is used for making simultaneous comparisons between two or more means of two or more related, not independent, groups.

However, in addition, it could be useful to apply a general linear mixed model that models for group means as fixed effects while simultaneously modeling for individual subject variables as random effects (12). This kind of model is a subject-specific model and is a choice for analysing longitudinal data. Unlike the repeated measures ANOVA, which requires a complete balanced array of data, the mixed model can accommodate a dataset with a large portion missing. Although the repeated measures ANOVA requires a fixed time schedule among all individual units, the mixed model can accommodate flexible time schedules. Furthermore, rather than treating time as a categorical variable, as in the repeated measures ANOVA, the mixed model is capable of treating time as either a continuous variable or a categorical variable or both.

Spearman's correlation coefficient measures the strength of association between two ranked variables.

Differences will be considered statistically significant if the p-value will be less or equal to a type I error =0.05 (two-sided test).

11. Efficacy data

a. Primary Endpoint Analysis

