The primary endpoint is to evaluate the changes from baseline in the score of convenience satisfaction domain of TSQM-9 at 12 weeks. (*Stata instruction: anova var1 time, repeated(time)*)

b. Secondary Endpoints Analysis

- Changes from baseline in the score of all domains of TSQM-9 at 24 weeks;
- Changes from baseline in patient adherence to study treatment survey at 12 and 24 weeks;
- Changes from baseline in the score of FSS (Fatigue Status Scale) at 12 and 24 weeks;
- Changes from baseline in the score of Adapted Sclerosis Treatment Concerns Questionnaire (MSTCQ) at 12 and 24 weeks;
- Changes from baseline in the score of Multiple Sclerosis International Quality of Life questionnaire (MusiQoL) at 12 and 24 weeks;
- Changes from baseline in clinical measures (ARR, percentage of relapse-free patients), measures at 24 weeks.

All the above primary and secondary endpoints will be analysed by a repeated measures analysis of variance adjusted for baseline factors (age, sex, disease duration, previous treatment duration, EDSS) (*Stata instruction: anova var1 var2 time, repeated(time)*).

Correlations between variables will be assessed by a Spearman rank correlation coefficient (*Stata instruction: spearman var1 var2*).

[figure not shown]
To evaluate the relationship between patients' satisfaction and social-demographic factors (age, sex, employment working, level of education, etc.) and clinical characteristics (ARR, disability, etc.) generalized linear mixed models for repeated measurements will be performed (*Stata instruction: mixed var1 var2 || patient:*).

12. Safety Data

a. Adverse events

All events will be coded using the Medical Dictionary for Regulatory Activities (MedDRA). Type and incidence of all AEs will be tabulated. Severity and drug relatedness of all reported AEs will be tabulated.

b. Clinical Laboratory Tests

	Statistical Analysis Plan Protocol N. BIIT0215– Platinum	Pag. 14 di 18
---	---	---------------

For the clinical laboratory data, descriptive statistics will be generated for all tests performed. Laboratory abnormalities will be determined in accordance with the normal ranges of the clinical laboratory. Laboratory abnormalities will be tabulated.

13. Tables

The following tables will be repeated for each visit, if applicable.

- P1. Number and percentage of patients enrolled per center
- P2. Number and percentage of patients stratified by gender; mean and median age, range and interquartile range;

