- P3. Number and percentage of patients stratified by race;
- P4. Number and percentage of patients stratified by educational level;
- P5. Number and percentage of patients stratified by working status;
- P6. Mean and median age, range and interquartile range of time since diagnosis of SM;
- P7. Number and percentage of patients undergoing pharmacological treatment for MS by active substance; mean and median, interquartile range and range of the dose and distribution of the frequency of treatment administration;
- P8. Number and percentage of patients undergoing concomitant pharmacological treatment by active substance; mean and median, interquartile range and range of the duration;
- P9. Mean and median, range and interquartile range of the total number of relapses from the diagnosis;
- P10. Mean and median, interquartile range and range of the total number of relapses in the last year;
- P11. Number and percentage of patients stratified for relevant previous and / or concomitant diseases; if previous, mean and median, range and interquartile range of duration; if ongoing, number and percentage of the diseases being treated;
- P12. Number and percentage of patients stratified by outcome (not performed / normal / abnormal) to physical examination in relation to:
 - a) General appearance;
 - b) Skin;
 - c) Head, neck, thyroid;
 - d) Ear, nose, throat;
 - e) Muscolo-skeletal;
 - f) Respiratory;

- g) Heart;
- h) Peripheral vascular;
- i) Gastrointestinal
- j) Abdomen, liver;
- k) Renal and genitourinary
- l) Endocrine / Metabolic
- m) Neurologic;
- n) Mental status;
- o) Other;

P13. Mean and median, interquartile range and range of height, weight and bmi value

P14. Mean and median, interquartile range and range of temperature, respiration rate, heart rate, maximum and minimum blood pressure;

P15. Mean and median, range and interquartile range of the number of episodes of acute exacerbation since the last visit;

P16. Mean and median, interquartile range and range of EDSS score;

P17. Mean and median, interquartile range and range of TSQM-9, all domains: effectiveness, convenience and global satisfaction;

P18. Change from baseline in the score of convenience satisfaction domain of TSQM-9 at 12 weeks;

P19. Change from baseline in the score of all domains of the TSQM-9 at 24 weeks;

P20. Adjusted repeated measures analysis of variance for change of convenience satisfaction domain of TSQM-9 at 12 and 24 weeks;

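### Both ANOVA commands in SAP section 11 omit the patient term, so as written they do not carry out the paired analysis that section 10 describes

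*SAP*

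**What the plan says.** SAP section 10 chooses a repeated measures ANOVA and describes it as a comparison of "two or more means of two or more related, not independent, groups". It adds that "it could be useful to apply a general linear mixed model". The two-sided significance level is 0.05.

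Section 11 turns this into Stata commands (the closing bracket falls outside the quotations):

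- 11.a, primary endpoint: "anova var1 time, repeated(time". The only model term is time.
- 11.b, adjusted analyses: "anova var1 var2 time, repeated(time". The accompanying sentence reads "All the above primary and secondary endpoints will be analysed by a repeated measures analysis of variance adjusted for baseline factors" and lists age, sex, disease duration, previous treatment duration and EDSS. So var2 stands for those factors.
- 11.b, relationship of satisfaction to patient characteristics: "mixed var1 var2 || patient". This is the only command that names the patient.

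Protocol sections 16.3.2 and 16.3.3 describe the same ANOVA and give no code. On the outcome variable, protocol 16.3.3 has "The primary endpoint (change of TSQM-9 convenience domain at week 12" and SAP table P20 has "Adjusted repeated measures analysis of variance for change of convenience satisfaction domain of TSQM-9 at 12 and 24 weeks". Neither document says whether var1 is the raw score or the change score. The sample size (SAP section 6, protocol 16.5) uses an SD of 16 for the within-patient difference between baseline and week 12.

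**The concern.** A repeated measures ANOVA gains its precision by removing differences between patients from the error. That requires a term that identifies the patient. Without one, the model cannot separate variation between patients from variation within them, and the visits are handled as independent samples.

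The 11.b sentence applies its command to the primary and all listed secondary efficacy endpoints, so the omission reaches every one of them. Followed literally, the commands either do not run or discard the pairing on which the sample size rests. The prose does not name the error term, and the obvious repairs do not all give the same week-12 test.

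**Working it through.** **1. Is the term supplied elsewhere?** The 11.a command has no placeholder that could stand for the patient. In 11.b the only spare placeholder is var2, which its own sentence assigns to the baseline factors. Reading var2 as the patient would drop the adjustment and leave 11.a unrepaired. The term is absent from both commands.

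**2. Inputs.** From the plan: n = 250, change of 3 points, SD of change 16, two-sided 0.05. Assumed: baseline SD 10 (entry requires a score below 58, which narrows the baseline spread) and week-12 SD of 12.5 to 16. The documents give no week-12 SD.

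**3. The plan's own power figure.** The standard error of the mean change is 16/√250 = 1.012. The paired test then has power Φ(3/1.012 − 1.96) = 84.2%, or 84.0% by the noncentral t. The plan states 90%. That is matched only by a one-sided 0.05 test (90.7%), which is a separate matter. The benchmark here is 84.0%.

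**4. Time alone fitted to raw scores at baseline and week 12.** The model's standard error is √((s0² + s1²)/250), with 498 residual degrees of freedom (critical value 1.965). The true SD of the estimated change remains 1.012. Hence:

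- power = Φ((3 − 1.965·SE)/1.012)
- type I error = 2·(1 − Φ(1.965·SE/1.012))
- implied correlation r = (s0² + s1² − 256)/(2·s0·s1)

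| SD baseline / week 12 | r | SE | Power | Type I error |
|---|---|---|---|---|
| 10 / 12.5 | 0.00 | 1.012 | 84.1% | 4.9% |
| 10 / 14 | 0.14 | 1.088 | 80.3% | 3.5% |
| 10 / 16 | 0.31 | 1.193 | 74.1% | 2.1% |

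A simulation of 20,000 trials at 10/16 gave 74% power and 2.0% to 2.1% type I error for time only. With a patient term over the same two visits it gave 84% and about 5%.

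**5. The adjusted command.** Baseline factors remove part of the between-patient variance. At 10/16, suppose they explain 10% of the pooled variance: SE = √(0.9·356/250) = 1.132 and power is 78%. At 20%: SE = √(0.8·356/250) = 1.067 and power is 81%. Both percentages explained are assumptions; the documents give none.

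**6. Adding the patient over all three visits with one pooled error.** The week-12 contrast then uses the mean of the three pairwise difference variances instead of its own 256. With assumed SDs 10/16/16 and correlation 0.31 between baseline and each later visit, that mean is (256 + 256 + 512·(1 − r))/3, where r is now the week 12–24 correlation. At r = 0.8 it is 204.8, so the type I error is 2·(1 − Φ(1.965·√(204.8/256))) = 7.9%. For r = 0.5, 0.6 and 0.7 it is 4.9%, 5.8% and 6.7%.

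**7. What var1 is.** If var1 held the change at weeks 12 and 24, the time term would compare week 24 with week 12, which is not the primary endpoint. Section 10 compares means over time, so the raw score at each visit is the coherent reading.

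**The case against.** The strongest reply is that the commands are shorthand and the prose governs. SAP section 1 presents the plan as general guidance. One var2 stands for five factors, so nobody could run the lines literally. The method, covariates, time point and significance level are all fixed in words, and the mixed command shows that the authors knew the grouping unit. Much of this stands: the intended analysis is clear, and this is a mismatch between code and text rather than a chosen unpaired analysis. What it leaves open is the error term, and step 6 shows that a natural repair can shift the week-12 test.

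A second reply is that the harm depends on software behaviour that the documents cannot show. That also stands. If the command stops, no wrong result is produced and the power figures do not apply.

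Two stronger readings are tempting. A reader might infer that the primary result would be a spurious benefit. The documents do not support this, because losing the pairing on positively correlated raw scores makes the time test conservative. A reader might also put the plan's SD of 16 at both visits and infer a much larger loss of power. That does not fit the entry rule, which admits only baseline scores below 58.

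**Conclusion.** The point holds as an error in the written commands: neither ANOVA line contains the patient term that section 10 and the sample size require. This can be read directly from the text.

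The consequence is less certain and modest. If time alone is fitted to raw scores, power for the unadjusted command lies between 84% (no loss) and 74%, against 84% paired, and the type I error lies between about 5% and 2%. At the lower end the adjusted command would have about 78% to 81%. These figures rest on a baseline SD of 10, a week-12 SD of 12.5 to 16, 250 complete pairs and, for the adjusted command, covariates explaining 10% to 20% of the variance. They do not apply if the software rejects the command or if var1 is a change score. No change to design or data collection is needed, but the commands should be corrected before the analysis is run.

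**What to change.** - Write the patient term in both commands; for the unadjusted one, for example, `anova var1 patient time, repeated(time)`.
- State that var1 is the raw score at each visit, and align the wording of table P20.
- In the adjusted analysis the five baseline factors are constant within a patient and so confounded with the patient term. State that they are tested against between-patient error, or fit the mixed model that section 10 allows with patient as the grouping level.
- Take the week-12 versus baseline contrast from those two visits, or from an unstructured within-patient covariance, rather than from one error pooled over three visits.

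The cost is a short SAP edit. Any move from ANOVA to the mixed model must be recorded and the protocol wording aligned. If the primary contrast uses only two visits, the week-24 contrasts need their own line. With complete pairs, main effects of patient-constant factors do not alter the week-12 contrast or its standard error, so little else in the primary result should change.

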## 4.2. Schedule of Events

Tests and assessment	T0 (Enrollment)	T1 (12 weeks) ± 1 week	T2 (24 weeks) ± 1 week	ET Early termination
Inclusion/Exclusion criteria	X			
Informed consent	X			
Social-demographics (e.g., age, gender)	X			
Medical history (e.g., disease duration, previous disease history and treatments)	X			
On-treatment medical information (e.g., concomitant therapies, comorbidities)	X	X	X	X
Pregnancy hCG test	X			
Clinical and neurological evaluation (including recording of relapses and EDSS)	X	X	X	X
Drug Supply	X	X		
Assessment of patients' satisfaction (TSQM-9)	X	X	X	X
Assessment of patients' adherence	X	X	X	X
Assessment of patients' injection-system satisfaction (Adapted MSTCQ)	X	X	X	X
Assessment of patients' HRQoL (MusiqoL)	X	X	X	X
Assessment of patients' fatigue (FSS)	X	X	X	X
Routine Laboratory tests	X	X	X	X
Adverse events, pregnancy exposure, episodes of overdose		X	X	X
Drug Accountability 		X	X	X

1. If a dose is missed, it should be administered as soon as possible, within 7 days.

CONFIDENTIAL

The information contained herein may not be used, disclosed, or published without the written consent of Biogen Italia

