### **7.2. Overall Study Duration and Follow-Up**

The overall study duration will be of 24 weeks, inclusive of baseline evaluation and treatment phase.

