## 13. EFFICACY ASSESSMENTS

### 13.1. Evaluations concerning the patients' adherence, quality of life, injection-system satisfaction, through the specific tests, including MSTCQ and MusiQoL.

Being this a health outcomes research study, in the present protocol the term *efficacy* refers to the assessment of the following patients' reported parameters, corresponding to the primary and secondary objectives of the study, and to the measurement of the related endpoints:

- overall treatment satisfaction;
- injection system satisfaction;
- adherence to treatment;
- health-related quality of life;
- fatigue.

Demographic (age, gender, education and employment) and medical information (disease duration, previous treatments, comorbidities and concomitant therapies, EDSS score and number of relapses in the previous 12 months) will be obtained at baseline.

All the endpoint-related questionnaires, described below, will be administered at baseline and after 12 and 24 weeks of treatment.

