Data for estimating the sample size were derived from studies reporting the distribution (mean value and standard deviation) of the TSQM-9 in MS patients treated with IFN (9). Assuming an average value of the overall convenience domain at baseline of 55 (SD=16) (9), with 250 subjects we have a power of 90% to detect a change of 3 points on the overall convenience domain (from 55 to 58) under the conservative hypothesis of a SD=16 (9) for the difference between baseline and week 12. However, by assuming a drop-out rate up to 10% during the study, we consider it appropriate to enrol a total of 275 patients.

7. Software

The analysis will be performed using the software Stata version 14.0.

8. Variables for analysis

This section contains definitions and conventions that will be used for the analysis.

Demographic and baseline characteristics

Demographic (age, gender, education and employment) and medical information (disease duration, previous treatments, comorbidities and concomitant therapies, EDSS score and number of relapses in the previous 12 months) will be obtained at baseline.

Efficacy

Being this a health outcomes research study, the term efficacy refers to the assessment of the following patients' reported parameters, corresponding to the primary and secondary objectives of the study, and to the measurement of the related endpoints:

- overall treatment satisfaction;
- injection system satisfaction;
- adherence to treatment;
- health-related quality of life;
- fatigue.

All the endpoint-related questionnaires, described below, will be administered at baseline and after 12 and 24 weeks of treatment.

Primary variables

a) Patients' Satisfaction assessment

- *Abbreviated Treatment Satisfaction Questionnaire to Medication (TSQM-9)*

The TSQM Version 1.4 is a 14-item psychometrically robust and validated instrument consisting of four scales. The four scales of the TSQM include the effectiveness scale (questions 1 to 3), the side effects scale (questions 4 to 8), the convenience scale (questions 9 to 11) and the global satisfaction scale (questions 12 to 14). In the TSQM-9, the five items related to side effects of medication were not included, which creates a need to psychometrically assess the performance of the abbreviated instrument.

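### Change from baseline in percentage relapse-free has no baseline window, and none of the candidate windows is comparable with 24 weeks on study

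*SAP*

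**What the plan says.** SAP section 11.b names the endpoint as "Changes from baseline in clinical measures (ARR, percentage of relapse-free patients), measures at 24 weeks". Protocol sections 6.2.2 and 16.1.2 use the same wording, and the protocol synopsis adds EDSS. The SAP then states: "All the above primary and secondary endpoints will be analysed by a repeated measures analysis of variance adjusted for baseline factors". A change from baseline needs a baseline value, but no section gives a look-back period for relapse-free status.

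The relapse data listed are:

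- **At baseline:** the "number of relapses in the previous 12 months" (SAP section 8; Protocol 13.1 has "EDSS score and number of relapses in the previous 12 months"). SAP section 13 tabulates the "total number of relapses from the diagnosis" (P9) and the "total number of relapses in the last year" (P10).
- **Schedule of Events (Protocol 4.2):** "Clinical and neurological evaluation (including recording of relapses and EDSS") is marked at T0, T1, T2 and early termination, with no look-back at T0.
- **On study:** table P15 counts exacerbations since the preceding visit. Protocol 7.2 says "The overall study duration will be of 24 weeks".

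Inclusion criterion 6 requires at least 30 relapse-free days before baseline. Among the SAP tables, P35 gives the annualised relapse rate (ARR); none gives percentage relapse-free.

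**The concern.** Percentage relapse-free depends on how long patients are watched. At any constant rate above zero, more patients are relapse-free over 24 weeks than over 12 months. If the endpoint is computed from the listed baseline count, it improves even though the switch of treatment does nothing to the relapse rate. A control group would show the same artefact and so cancel it, but this study has one arm.

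The SAP tests at two-sided 0.05 and says its results are for publication. A significant gain in percentage relapse-free could therefore be read as an effect on disease activity, which is a stated secondary objective. Because the window is unstated, the choice among baselines that push the result up or down could also be made after the data are seen.

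**Working it through.** The documents give no planning rate, percentage or power for relapse-free status, so there is no figure of the plan's own to reproduce. The check asks what change appears when the relapse rate does not change.

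**Inputs**

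- Time on study: 24/52 = 0.462 year (Protocol 7.2).
- Baseline time at risk: 1 year for the 12-month count; 335/365 = 0.918 year once criterion 6 removes 30 days; (168 − 30)/365 = 138/365 = 0.378 year for a 24-week look-back.
- Illustrative rate: 0.256 relapses per year with a proportion relapsed at one year of 0.187 (every-2-weeks arm of the Phase 3 study, Protocol 5.1). An assumed range of 0.2 to 0.5 per year is also run.
- n = 250, two-sided 0.05 (SAP sections 6 and 10).

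**Formulas.** For rate m and time T, the relapse-free probability is exp(−mT) under Poisson, or (1 + k·m·T)^(−1/k) under a negative binomial with dispersion k. Setting 1 − (1 + 0.256k)^(−1/k) = 0.187 gives k = 1.98.

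**12-month baseline at 0.256 per year** (points computed before rounding)

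| Model | Baseline, 12 months | Baseline, 335 days | 24 weeks on study | Rise, 12 months | Rise, 335 days |
|---|---|---|---|---|---|
| Poisson | 77.4% | 79.1% | 88.9% | +11.4 | +9.8 |
| Negative binomial, k = 1.98 | 81.3% | 82.5% | 89.9% | +8.6 | +7.5 |

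Over rates of 0.2 to 0.5 per year and k from 0 (Poisson) to 2, the rise runs from +6.4 (0.2, k = 2, 335 days) to +18.7 (0.5, Poisson, 12 months).

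**24-week look-back.** Poisson at 0.256: baseline exp(−0.256 × 0.378) = 90.8% against 88.9%, a change of −1.9 points. Over the same range of rates and k it is −1.3 to −3.4. The windows look equal, but the baseline one has 30 days in which entry rules out a relapse.

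**30-day baseline.** Every eligible patient is relapse-free, so baseline is 100% and the change at 0.256 per year is about −11 points (Poisson: 88.9 − 100) or −10 (negative binomial: 89.9 − 100).

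**Chance of a significant result with no effect.** In simulated trials of 250 patients at 0.256 per year with a 12-month baseline, an unadjusted paired t test is significant in about 67% to 93%. The figure depends on dispersion, on criterion 6, and on whether a patient's relapse propensity is shared across periods. Repeat runs move these limits by a point or two. With equal windows and no stability rule it is about 5%. Adjusting for fixed baseline factors would not remove a shift between periods that applies to everyone.

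**ARR for comparison.** Dividing by time removes the effect of window length. Criterion 6 still lowers a 12-month baseline ARR by 30/365 = 8%: 0.256 × 335/365 = 0.235, a null ratio of on-study to baseline rate of 1.09, unless 335 days is the denominator.

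**The case against.** The documented fault is an omission. The 12-month count is listed as a baseline characteristic and no section assigns it to this endpoint. The schedule records relapses at T0 without a window, so another choice is not ruled out. This stands, and a reader who infers that the plan prescribes a 12-month baseline, or that the percentage must rise, goes beyond the text. But every candidate window examined is biased at a constant rate; only the direction differs.

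The size is borrowed. In the cited study 83% of patients were treatment-naïve and all had a relapse in the prior year, whereas these patients are already on interferon. This also stands: the figures illustrate. Since criterion 6 applies to everyone and the Poisson model does not reproduce that study's 18.7% relapsed, +7.5 is the figure best matched to the documents.

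On-study time is not exactly 24 weeks. Baseline may precede the first dose by up to 2 weeks (Protocol 7.1) and T2 has a 1-week tolerance, so T0 to T2 can reach 24 + 2 + 1 = 27 weeks. At 27 weeks the matched rise is still about +6.4.

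No listed table reports relapse-free status, so a reader might overstate matters by saying that the table list already commits to the misleading result. It does not; the commitment is in the text of section 11.b. The simulated rejection rates also assume a patient-level paired test that the SAP does not spell out.

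One might extend the argument to ARR, to adherence or to the primary endpoint. The documents do not support this. ARR is annualised. For adherence, the scoring in Appendix C is not shown, P21 and P23 tabulate missed and expected injections, and fewer injections are the protocol's intended route to better compliance. The primary endpoint is a questionnaire score with no look-back of this kind in the plan.

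**Conclusion.** The point holds for percentage relapse-free alone. The plan calls for a change from baseline whose baseline is undefined, and no window that the documents suggest gives a fair comparison with the on-study period. With the 12-month count, the artefact is about +7.5 points at the best-matched illustrative values and about +6 to +19 over assumed rates of 0.2 to 0.5 per year. With a 24-week look-back it is about −1.3 to −3.4 points.

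That the 12-month version rises needs only a constant rate above zero. The sizes rest on the assumed rates and dispersion, and use of the 12-month count is an inference. This is a secondary endpoint that should be corrected before analysis.

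**What to change.** 1. Remove percentage relapse-free from the change-from-baseline ANOVA. Report it as a 24-week on-treatment proportion, with the number of patients observed for the full period, and add a table for it.
2. Base the change in disease activity on ARR, using a Poisson or negative binomial model for repeated counts per patient with log(time at risk) as offset. Use each patient's actual on-study time, and about 335 days for the 12-month baseline because of criterion 6.
3. Optionally, compare relapse-free status in days 31 to 198 before baseline with the first 168 days on study, which gives 168 days at risk in each. Do this only if both the date of the last relapse before baseline and the dates of on-study relapses are recorded; the documents do not show that they are.

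Items 1 and 2 need small changes to SAP wording and code, and no data beyond the listed relapse counts and visit dates. The cost is that the reported change will look less favourable than one set against 12 months.
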